### **12.2.2 Final Analyses**

Preliminary analyses will be conducted to describe the collected variables. Univariate descriptive statistics and frequency distributions will be calculated, as appropriate for all collected variables along with two-sided 95% confidence intervals. The primary endpoint, Day 1 PDRPeak will be compared between those that spontaneously survive (SS) by Day 21 and those that either die or receive a transplant by Day 21 with a logistic regression model at a two-sided alpha level of 0.10. All enrolled patients with a value at Day 1 will be included in the analysis. The primary analysis will not stratify by non-APAP ALI/ALF but exploratory analyses will be conducted that examine potential differences as described below. It is not anticipated that any enrolled patient will be missing the outcome of SS.

There are several exploratory aims that will be conducted for future hypothesis generation. In addition to the comparison of mean PDRPeak values between the two cohorts, a cutpoint for the PDRPeak value will be examined using a receiver operating curve. The identified cutpoint will be compared to other known prognostic indices including Kings College criteria (KCC), Model of End-Stage Liver Disease (MELD), and the ALFSG-PI (prognostic index). As a secondary analysis and where serial measurements are available, the trends in the MBT results (PDRPeak, PDR20, CPDR20) will be related to outcome (Day 21 SS) using repeated measures analysis. A multivariable regression will be performed to assess if PDRPeak, in combination with traditional prognostic measures provides an accurate prediction of Day 21 outcome. These pre-specified exploratory analyses will be conducted using a significance level of 0.05.

With the inclusion of non-APAP ALI patients, we will conduct exploratory subgroup analyses and examine the association with MBT results for each subgroup (non-APAP ALI and ALF). Based on current registry enrolments, we anticipate the study population to consist of 17-20% non-APAP ALI enrollments. A total of 35-40 non-APAP ALIs will not provide definitive evidence but will provide further hypothesis generating information. For the non-APAP ALI subgroup, we will also examine the PDR peak when poor outcome is defined as progression to ALF, transplant or death within 21days. Point estimates and confidence intervals will be used for interpretation of these analyses more than pvalues due to the exploratory nature of the analyses. We anticipate roughly

10% will convert to ALF. All statistical analyses will be conducted using SAS V9.2 or higher (SAS Institute, Inc., Cary, NC). The specified analyses will be repeated as an exploratory aim with the Day 7 outcome of SS.

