### 3 INTRODUCTION

#### 3.1 Background and Rationale

The importance of identifying the patient with ALI or ALF who is likely to die without a liver transplant cannot be overstated and has remained a primary focus of clinical investigation for 25 years. A recent analysis also conducted by the Acute Liver Failure Study Group (ALFSG) found that poor outcomes in the ALI patients are less frequent than is observed in the ALF population. However, in cases where ALI was not related to an acetaminophen (APAP) overdose, progression to poor outcomes was similar: 41% of patients with non-APAP ALI progressed to ALF, transplant and/or death compared to 7% of patients with APAP ALI (1). Unfortunately, analyses have shown that the King's College Criteria (KCC) are inaccurate predictors of prognosis. Clinically based criteria such as the Sequential Organ Failure Assessment (SOFA) and Acute Physiology and Chronic Health Evaluation II (APACHE II) scores offer improved but still inadequate accuracy (2-4). These traditional scoring systems and prognostic models currently used to monitor patients with ALF lack individual sensitivity and specificity and do not provide direct information about the liver's metabolic function, which is a key variable in assessing liver status and potential disease progression versus recovery in ALF patients. The Acute Liver Failure Study Group (ALFSG) completed an analysis of predictors of outcome in the largest cohort ever studied, 1,974 patients, half of whom were randomly assigned to participate in a model development cohort, and half in a validation cohort (5). The ALFSG Prognostic Index (ALFSG-PI) identified coma grade, ALF etiology, vasopressor use, and the log transformations of admission bilirubin and INR as independent clinical predictors of spontaneous survival in patients with ALF, with a c-statistic of 0.84 by AUROC curve analysis. The ALFSG-PI was also significantly better than Model for End-Stage Liver Disease (MELD) score (0.70) or KCC (0.65). The group also developed a prognosis index for ALI patients that identified etiology, admission values of bilirubin, INR, APAP level and duration of jaundice prior to enrollment as variables associated with prediction of progression to ALF, transplant or death within 21 days (1). The ALI prognosis index had a c-statistic of 0.84. Despite these advances, better predictive modalities are still needed.

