### **3.2 Summary of BreathID® and MBT Clinical Data**

The BreathID® MBT has been used to assess the functional capacity of the liver in several clinical situations. In a study of 165 patients with cirrhosis which included two ALFSG sites, MBT predicted liver-related death and the appearance/exacerbation of ascites better than the Model for End-Stage Liver Disease (MELD) score (6, copy attached).

MBT has also been used in a pilot study of patients with ALF performed at Kings College Hospital and in Israel (7). Sixty-two patients with severe ALI/ALF of diverse etiologies were followed with the MBT during the acute phase of their illness. During their hospital course, 62% of patients spontaneously survived, 21% underwent liver transplantation, and 18% died with a mean follow-up of 7 days after baseline testing. In patients who spontaneously recovered, admission PDR and CPDR at 20 minutes after Methacetin ingestion were higher than those who died or underwent liver transplantation, with p-value of approximately 0.08 for the difference for both indices. Moreover, in the 38 patients in whom post-admission MBTs were available, PDR20 and CPDR20 were both much higher in spontaneous survivors (SS) than those who died or underwent transplant (p=0.0002 and 0.001, respectively), as were the changes in both parameters between Day 1 and Day 2-4. (The choice of the later day was not standardized. Values were used in the following order of preference depending upon their availability: Day 3, Day 4, or Day 2, if neither Day 3 nor 4 were available). Subgroup analyses clearly showed that patients who died or underwent transplant had similar PDR20 and CPDR20 on Day 1, but both were significantly lower than SS. These data strongly support the hypothesis that the MBT may assess the severity of ALF at

admission and the likelihood of hepatic recovery within 7 days of admission more accurately than laboratory tests regardless of the etiology of liver injury.

**Table 1. Methacetin breath test (MBT) results in 62 patients with ALI/ALF on admission (Day 1) and in 38 patients at one time point after admission (Day 3, or Day 2 or 4 if Day 3 is missing).**

MBT Parameter	Day	N	Total Population	Spontaneous Survivors	Death/ Transplant	P*
			Mean±SD/ Median[range]	Mean±SD/ Median[range]	Mean±SD/ Median[range]	
PDR 20	1	62	2.60[-1.71 - 33.02]	3.31[-1.71 - 13.52]	1.13[-1.22 - 12.80]	0.088

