#### **4.2.2 Secondary Endpoints**

1. Using the Day 1 PDRPeak as a continuous variable, we will determine a cut point value that best distinguishes between those that do and do not spontaneously survive at Day 21.

2. There are several exploratory aims that will be conducted for future hypothesis generation. These analyses include: assessing the change in MBT measurements (CPDR20, PDRPeak, PDR20 and CPDR30) over a maximum of 7 days from enrollment; assessing the relationship between single time points of MBT measurements (PDRPeak, PDR20 and CPDR20) and clinical outcome (both early and late outcomes, Day 7 and Day 21 SS); and, evaluating the use of the PDRPeak as a prognosis for Day 7 and Day 21 SS either alone or in conjunction with other clinical parameters including etiology, laboratory measurements and other available prognostic indices.

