## **5 INVESTIGATIONAL PLAN**

### **5.1 Study Design**

This is a multicenter, open label, non-randomized study of the MBT to assess functional trends of liver metabolism in patients diagnosed with ALI not related to acetaminophen overdose and patients diagnosed with ALF. The Breath Test will be performed up to five times on all enrolled subjects. The first Breath Test will be performed upon admission into the study (Day 1) and repeated on Days 2, 3, 5 and 7, as close to the same time of day as possible provided no contraindications are present. If an enrolled ALI or ALF subject receives a liver transplant, is discharged/transferred from the hospital or dies prior to Day 7, no additional Breath Tests will be performed. The study ends after the subject has been contacted to determine Day 21 spontaneous survival, transplantation and occurrence of serious adverse events since the last Breath Test.

If a subject who is enrolled into the ALFSG-MBT Trial with ALI converts to ALF, breath test collection will continue until a maximum of five Breath Tests have been performed. Once the ALI subject has been enrolled into the ALFSG Registry with ALF, subsequent Breath Tests should be performed as close to the same time of day as the previous Breath Tests provided no contraindications are present.

Site principal investigators (PIs) and clinical staff will be blinded to the results of the MBT so that there cannot be any reliance on the MBT for clinical decision-making.

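### The exploratory comparison of the MBT with KCC, MELD and ALFSG-PI should show transplant and death separately, because only the MBT is shielded from transplant decisions

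*Combined protocol and SAP*

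**What the plan says.** Under Section 12.2.2 (Final Analyses), the primary analysis relates Day 1 PDRPeak to Day 21 spontaneous survival (SS). The contrast group is "those that either die or receive a transplant by Day 21 with a logistic regression model". Section 4.2.2 sets the cutpoint on the same outcome: the aim is to "determine a cut point value that best distinguishes between those that do and do not spontaneously survive at Day 21". Section 12.2.2 then says that the "cutpoint will be compared to other known prognostic indices including Kings College criteria (KCC), Model of End-Stage Liver Disease (MELD), and the ALFSG-PI". It adds a multivariable regression that combines PDRPeak with traditional measures. Both are labelled exploratory.

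Section 5.1 states that site investigators and clinical staff are "blinded to the results of the MBT so that there cannot be any reliance on the MBT for clinical decision-making". Section 8.1 repeats the blinding, again for the MBT only. Section 11.1 has sites collect daily the clinical and laboratory data from which the indices are derived. Section 3.1 speaks of "traditional scoring systems and prognostic models currently used to monitor patients with ALF". The synopsis leaves care to institutional standards, and the note to exclusion criterion 10 (Section 6.2) lets patients already listed for transplant enrol.

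No analysis in Section 12.2.2 separates transplant from death. The extra poor-outcome definition for the non-APAP ALI subgroup also includes transplant.

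**The concern.** Transplant is a treatment decision, and the two sides of the comparison stand differently towards it. By design the breath test cannot affect who is transplanted. INR, bilirubin, coma grade and the other inputs of the indices are in the treating team's hands. If those inputs carry weight in the decision, the indices are scored partly against an outcome that they helped to produce.

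At stake is how the comparison is read. Section 3.2 hopes that the MBT may prove superior to current prognostic models. A breath test that predicts death as well as MELD or ALFSG-PI could look worse only because those indices follow transplant decisions, and the planned output would not let a reader see this.

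**Working it through.** The plan gives no figure on this point to reproduce. The check has four steps.

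**1. Is the asymmetry in the documents?** Transplant as failure: yes (12.2.2). Comparison with the three indices on that outcome: yes (4.2.2, 12.2.2). Blinding limited to the MBT: yes (5.1, 8.1). Index inputs known at the site: yes (11.1). A statement that the indices or their inputs determine transplant: no.

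**2. How much of the outcome could be transplant?** Section 3.2 reports for the pilot that "62% of patients spontaneously survived, 21% underwent liver transplantation, and 18% died".
- Share of failures: 21/(21 + 18) = 54%.
- Pilot rates at N = 200: 0.21 × 200 = 42 transplants and 0.18 × 200 = 36 deaths, so 78 failures. Non-transplanted patients: 200 − 42 = 158, of whom 36 die.
- If half of the 200 patients failed (an assumption; Section 12.1 uses 0.50 only for the mean MBT value) and the pilot split held: 100 × 21/39 = 54 transplants and 46 deaths.

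**3. How large could the artefact be?** This is an illustration with assumed inputs. Severity L is standard normal. The index K and the breath test B are each ρL + √(1 − ρ²) × independent noise, so they are equally accurate. A patient would die without transplant if 0.8L + 0.6 × noise exceeds a threshold. The transplant score is wK + (1 − w)C, where C is a separate clinical signal as accurate as K. It is standardised, multiplied by 0.8, and 0.6 × noise is added. The top 21% are transplanted, and the threshold is set so that 18% die without transplant.

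| Weight w on index | ρ = 0.5: AUROC index / MBT | Gap | ρ = 0.7: AUROC index / MBT | Gap |
|---|---|---|---|---|
| 0 | 0.66 / 0.66 | 0.00 | 0.75 / 0.75 | 0.00 |
| 0.25 | 0.71 / 0.67 | 0.04 | 0.78 / 0.76 | 0.02 |
| 0.5 | 0.76 / 0.67 | 0.08 | 0.81 / 0.76 | 0.05 |
| 0.75 | 0.79 / 0.67 | 0.12 | 0.83 / 0.76 | 0.07 |
| 1 | 0.80 / 0.66 | 0.14 | 0.84 / 0.75 | 0.09 |

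These AUROCs are against transplant or death. Against death without transplant, which cannot be observed in transplanted patients, the two markers stay equal (about 0.69 and 0.77). A variant of the model gave gaps from 0.03 to 0.15.

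A rerun of the same model, split by type of failure, shows where the gap arises. For w above 0, the index leads by 0.05 to 0.28 for transplant versus SS. For death versus SS it trails by 0.01 to 0.03. Another variant put the reversal among non-transplanted patients at up to 0.05.

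For scale, Section 3.1 gives 0.84 for ALFSG-PI, 0.70 for MELD and 0.65 for KCC, so differences of 0.14 and 0.05. The artefact could be of that order.

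**4. Can the non-transplanted subset decide the matter?** No. It selects on an event after baseline, and step 3 shows that this can reverse the bias. With 36 deaths among 158 patients, the AUROC difference has a standard deviation of about 0.06 to 0.07, as large as many of the gaps at issue.

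**The case against.** The strongest objection is that the causal link is missing. Section 3.1 says that the traditional models are used to monitor patients, not to list or transplant them. That sentence follows a discussion of KCC, SOFA and APACHE II; ALFSG-PI is the study group's own index, and nothing says that clinicians act on it. At zero weight the gap is zero. This stands, and it makes the size conditional.

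A reader might infer that the comparison is biased towards the existing indices. The documents do not support so firm a direction. The MBT cutpoint is chosen on the data in which it is compared, which favours the MBT. Section 3.2 says that treatment can obscure INR, bilirubin and encephalopathy grade, which would weaken the indices.

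A reader might also infer that the primary result is compromised, or that a test of added value is. Neither follows. The primary test has no comparator. The multivariable aim is prediction by PDRPeak together with traditional measures; no incremental-value test is stated.

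Pooling also has some support. Section 3.1 describes ALFSG-PI as built to predict spontaneous survival, and the pilot reported similar Day 1 PDR20 and CPDR20 in patients who died and in those transplanted. The 54% is borrowed as well: the pilot had 62 patients at King's College and in Israel and a mean follow-up of 7 days, whereas this trial is in the United States and runs to Day 21. These points argue for keeping the composite. They do not argue against showing its parts.

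**Conclusion.** The point holds as a cheap improvement, confined to the exploratory index comparison and multivariable model in Section 12.2.2. The asymmetry is in the documents; its effect is not. If the inputs of the indices influence transplant, the composite may favour the indices by roughly 0.02 to 0.15 in AUROC over the weights simulated (a quarter to all of the decision). If they do not, the artefact is zero. These sizes rest on an assumed model and on pilot rates, and with the opposing influences the net direction is not settled. As planned, the comparison cannot tell an index that predicts death better from one that tracks transplant decisions.

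**What to change.** Keep Day 21 SS as the outcome and add the following to Section 12.2.2.

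1. Describe Day 1 PDRPeak and each of KCC, MELD and ALFSG-PI in three groups: SS, transplanted, and died without transplant. Give discrimination with confidence intervals for transplant versus SS and for death versus SS. An index advantage that comes only from transplant is then visible.
2. Repeat the comparison and the multivariable model in non-transplanted patients, as a sensitivity analysis only. State that it selects on a post-baseline event, can be biased in the opposite direction, and has few deaths (about 36 of 158 on pilot rates). The death-versus-SS contrast in item 1 uses these same patients and needs the same caveat.
3. State that a difference from an index seen only on the composite cannot be read as better or worse prediction of death.

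Do not require the composite and non-transplant analyses to agree in direction before a claim is made. In simulations at N = 200 on pilot rates, with the MBT truly better by about 0.05 in AUROC, both analyses favoured it in 74 to 76% of trials at weight 0, 26 to 30% at 0.5 and 1% at 1. Such a rule would mostly suppress a breath test that is in fact better.

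The cost is wording and a few extra runs. Survival and transplantation are already recorded to Day 21, so no new data are needed. The downside is wide intervals.

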## 8.5 Schedule of Assessments

	Screening/ Subject Enrollment	Day 1	Day 2	Day 3	Day 5	Day 7	Day 21
Demographics	X						
Medical History	X						
Confirm Eligibility Criteria ^	X						
Prior Medications	X						
Concomitant Medications		X	X	X	X	X	
Grade of HE	X	X	X	X	X	X	
Labs (lactate, bicarbonate, INR, total bilirubin, phosphate, Creatinine, WBC, Platelet count, ammonia-arterial or venous (if clinically indicated))		X	X	X	X	X	
RRT (record time/tx prior to MBT)		X	X	X	X	X	
MBT		X	X	X	X	X	
Serum for APAP and APAP-adduct levels*		X	X	X	X	X	
AE Reporting		X	X	X	X	X	(SAEs only)
End of Study							X
Collection of data for MELD, KCC, and ALFSG- PI	X	X	X	X	X	X	

\* Only in the first 20 consecutive ALF subjects enrolled

^ In women of child-bearing potential; Urine pregnancy test or blood human chorionic gonadotropin (hCG) is acceptable.

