## **11 DATA MANAGEMENT**

### **11.1 Data Handling**

The raw data from the individual tests on the BreathID® MCS device will be analyzed using Exalenz's trending software. This program provided by Exalenz will combine all tests for any given subject bearing the same identification number and will plot the trend of the breath test results with the percent change displayed. This analysis will be carried out only after the subject has completed his/her participation in the study and in order not to bias the treating physician, the results will not be shared until the study is completed.

For all other study data, sites will enter case report form data into the password protected study database housed in WebDCU™. The WebDCU™ is a validated web-based clinical trials

management system that provides the infrastructure for real-time data capture and data sharing and includes designated web servers and supporting database servers. This user-friendly web-based database system will be used for subject enrollment, data entry, data validation, project progress monitoring, user customizable report generation, and secure data transfer. The web-based data capturing system allows for study data to be directly entered into the study specific database by the site via a secure internet connection. Secure Socket Layer (SSL) is used for data encryption. The web system combines all study tools into one system which includes study database, online training and help desk, subject calendar, electronic data clarification request (DCR) process, data entry, case report form (CRF) and participate tracking system, audit trail, and report generation mechanisms. This is the system used for the currently ongoing ALFSG Registry. Clinical and laboratory data will be collected by the site in order to derive MELD, ALFSG-PI, ALI-PI and KCC scores on a daily basis. These clinical data and laboratories are mandatory as they will be needed for calculation of the clinical outcome predictor indices.

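### The PDRPeak cut point is tuned by ROC on the study patients and then compared with KCC in the same patients, with no optimism correction planned

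*Combined protocol and SAP*

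**What the plan says.** Section 4.2.2 gives the first secondary endpoint: "we will determine a cut point value that best distinguishes between those that do and do not spontaneously survive at Day 21". It does not state the criterion for the best cut.

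Section 12.2.2 says the cut point will come from a ROC curve on the study data, and continues: "The identified cutpoint will be compared to other known prognostic indices including Kings College criteria (KCC", followed by MELD and the ALFSG-PI. No metric and no test is named for this comparison.

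The comparators come from the same patients. The schedule in Section 8.5 has a row headed "Collection of data for MELD, KCC, and ALFSG"-PI, marked at screening and on every breath-test day. Section 11.1 has sites collect data "in order to derive MELD, ALFSG-PI, ALI-PI and KCC scores on a daily basis". Section 12.2.2 does not say which day's KCC is used.

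On status, Section 12.2.2 says "There are several exploratory aims that will be conducted for future hypothesis generation" and "These pre-specified exploratory analyses will be conducted using a significance level of 0.05". It also plans a multivariable regression asking whether PDRPeak "in combination with traditional prognostic measures provides an accurate prediction of Day 21 outcome".

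Nowhere is there a split sample, cross-validation, bootstrap or external validation for the cut point. The development and validation cohorts in Section 3.1 belong to the earlier ALFSG-PI work.

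**The concern.** A cut chosen because it separates outcomes best in a sample will look better in that sample than in new patients. KCC is not re-tuned on these patients and gets no such benefit. The two are therefore compared on unequal terms, and the error always favours the breath test.

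Two results are affected: any sensitivity and specificity reported for the cut point, and the ranking of the breath test against KCC. A later study would probably adopt this cut, so its accuracy should not be inflated in a known direction. The multivariable regression needs no cut point, but it does not correct either result.

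For MELD and the ALFSG-PI the point is narrower: the plan does not say whether they are compared as continuous scores or at cut points.

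**Working it through.** The plan gives no figure for the cut point or for its comparison with KCC, so there is nothing to reproduce. The size was found by simulation.

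**Inputs from the documents**
- N = 200, with 50% spontaneous survival at the mean marker value (Section 12.1), used here as the overall rate.
- 17–20% non-APAP ALI (Section 12.2.2), so ALF patients number 200 × 0.80 = 160 to 200 × 0.83 = 166.
- 62% survival in the pilot (Section 3.2), used as a sensitivity case.
- c-statistics from an ALF cohort (Section 3.1): "The ALFSG-PI was also significantly better than Model for End-Stage Liver Disease (MELD) score (0.70) or KCC (0.65").

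**Assumptions**
- The cut maximises the Youden index, J = sensitivity + specificity − 1.
- The marker is normal with equal variance in the two outcome groups.
- The within-group correlation between the breath test and KCC is 0, 0.3 or 0.6.

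**Step 1: KCC.** For a yes/no rule the c-statistic is (sensitivity + specificity)/2. So J = 2 × 0.65 − 1 = 0.30.

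**Step 2: an equally good breath test.** With group means d apart, the best J is 2Φ(d/2) − 1. Setting this to 0.30 gives Φ(d/2) = 0.65 and d ≈ 0.77. The AUROC is Φ(d/√2) ≈ 0.707.

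**Step 3: sampling SD of the paired difference with both cuts fixed.** At correlation 0 and 100 patients per outcome group, the variance is 2 × (2 × 0.65 × 0.35)/100 = 0.0091, so the SD is 0.095. The simulation gives 0.096, 0.086 and 0.073 at correlations 0, 0.3 and 0.6.

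**Step 4: search the cut in the same sample** (6,000 trials per row). Ranges run over the three correlations. Brackets show the result with a pre-fixed cut. The last column applies only if a paired test at 0.05 were used; the plan names none.

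| Scenario | Apparent J | True J of chosen cut | Mean gain over KCC | Breath test ahead | Paired test favours breath test |
|---|---|---|---|---|---|
| n = 200, 50% survival | 0.347–0.348 | 0.286 | 0.047–0.049 | 70.6–75.6% (50–51%) | 7.3–8.0% (2.5–2.9%) |
| ALF only, n = 160–166 | 0.352–0.355 | 0.284 | 0.051–0.054 | 70.2–76.5% | 6.6–8.6% (2.4–2.8%) |
| 62% survival, n = 200 | – | – | 0.048–0.050 | 70.0–75.7% | – |
| 62% survival, n = 163 | – | – | 0.056–0.059 | 70.2–78.3% | 7.0–9.1% |
| KCC correct in 90% of survivors and 40% of poor outcomes (assumed; J = 0.90 + 0.40 − 1 = 0.30), n = 200 | – | – | 0.048–0.049 | 72.1–76.9% | 7.3–9.0% (2.9–3.0%) |
| Breath test truly 0.05 worse (best J 0.25), n = 200 | 0.300–0.301 | – | about 0 | 49.1–50.6% (26.6–29.0%) | 1.8–2.1% |

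**Step 5: bias relative to noise** (n = 200, 50% survival). At correlation 0, 0.049/0.096 = 0.51. At 0.6, 0.048/0.073 = 0.66. The lean is half to two thirds of a sampling SD.

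**Step 6: a different model.** With a logistic outcome, n = 200 and an odds ratio of 1.5 per SD (Section 12.1 does not state the unit), apparent J is 0.216 and true J is 0.144, so the optimism is 0.072. The optimism is 0.086 at an odds ratio of 1.0 and 0.060 at 3.0. Against a fixed rule of equal best J, at odds ratios of 1.5 to 3.0, the mean gain is 0.046–0.059. A paired test favours the breath test in 6.3–7.7% of trials, against 2.1–2.4% with a pre-fixed cut.

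**The case against.** The strongest objection is that the ranking figures assume a near-tie, where a small shift matters most. At the design odds ratio of 1.5 per SD (AUROC about 0.61) against a KCC Youden index of 0.30, the breath test's apparent index is about 0.215. It still trails by about 0.085, and it is ahead in only 11–17% of trials (3–7% with a fixed cut). At AUROC 0.80 it is ahead in 94–98% of trials with a fixed cut and 98–99.7% with a searched one. This stands: the bias stays near 0.04–0.06 throughout, but it decides the ranking only when the two methods are close.

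Second, the simulated analysis is a reading of the plan. The plan names no Youden rule, difference measure or test, and promises no sensitivity or specificity for the cut. That KCC is a fixed rule is inferred from its being an established criterion. These are fair limits. However, the text compares the identified cut point itself, so a later choice of AUROC would be a change to the plan rather than a reading of it.

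Third, the analysis is exploratory, and breath-test results are withheld from site investigators and clinical staff. This limits the consequence. Yet Section 4.2.2 lists the cut point as a secondary endpoint and Section 12.2.2 calls the analyses pre-specified, so the missing rule and correction are worth supplying.

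Finally, one could simply label the accuracy as apparent and in need of external validation. That would be honest, but the KCC comparison would stay uneven.

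**Conclusion.** The concern holds. As written, the plan tunes the breath-test cut on the study patients and sets it against an untuned rule in the same patients, with nothing to offset the advantage. With 200 patients and two equally good methods, the cut's Youden index is overstated by about 0.06 (0.35 against 0.29) and the comparison leans by about 0.05. A breath test truly 0.05 worse than KCC would look level.

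This shifts the estimate without dominating it. It rests on the Youden rule, a normal marker and KCC taken as a fixed rule with a c-statistic of 0.65. The rejection rates are conditional on a test that the plan does not name. The primary analysis of continuous Day 1 PDRPeak is unaffected. The change should be made because it is cheap and the bias has a known direction; the trial's main conclusion does not depend on it.

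**What to change.** **1. Cut point and KCC.**
- Name the cut-point rule.
- Report bootstrap optimism-corrected sensitivity and specificity, repeating the search in every resample. For J, the corrected value is apparent J minus the mean over resamples of (J of the resample's cut in that resample − J of the same cut in the full sample).
- Compare the corrected figures with KCC scored on Day 1, and state whether all patients or only ALF patients are used.
- Give a 95% bootstrap interval for the paired difference, re-centred on the corrected difference. Do not use a plain percentile interval that re-searches the cut: it favours an equally good breath test in 12–18% of trials, worse than no correction.

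**2. MELD and ALFSG-PI.** Compare continuous Day 1 PDRPeak with Day 1 MELD, and with Day 1 ALFSG-PI in the ALF patients, by paired AUROC difference with a 95% confidence interval.

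**Performance of the first change** (2,000 trials × 300 resamples, n = 200, equally good methods). Corrected J is 0.302–0.304 against 0.299–0.301 for KCC. The gain is 0.003–0.005 and the breath test is ahead in about 52% of trials. For a breath test truly 0.05 worse (correlation 0.3), the corrected difference is −0.047 and it is ahead in 28%.

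**Cost.** SAP wording and a short program on data already collected; no new patients or visits. The reported accuracy becomes slightly less favourable. The correction is not complete: about 0.02 of optimism remains in the cut's own accuracy. The re-centred interval covers 92–93% and favours an equally good breath test in about 4% of trials (nominal 2.5%). Intervals are wide: ±0.13 to 0.17 for the Youden difference from KCC, and about ±0.06 to 0.10 for the AUROC differences.
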